8.2.1.4 Adverse Events by Preferred Terms (AEs/ADRs/SAEs)

All AEs recorded in CRFs will be classified into the system organ class (SOC) and the terms of AE will be coded according to the classification of AEs in 'MedDRA'. All AEs, except for 'Unlikely', will be considered as AE whose causal relationship to study drug cannot be excluded (hereinafter "Adverse Drug Reaction (ADR)").

- The number and percentage of AE will be presented overall and by preferred term. This will be repeated by:
 - Severity
 - Measures taken in relation to Duavive tab.
 - Other measures
 - Seriousness
 - Outcome
 - Causal relationship of the adverse event with the study drug
 - Other causal relationship of the adverse event with the study drug
- The number of subjects and the number of unexpected AE/ADR, Serious AE (SAE)/Serious ADR (SADR), unexpected SAE/SADR, AE/ADR will be calculated according to the preferred terms. Also, the proportion of subjects to whom AE/ADR occurred will be estimated. In re-examination report, SAE/SADR and unexpected AE/unexpected ADR in accordance with preferred terms will be presented respectively according to the frequency categories of adverse events in the approved local label.
- The subjects with SAE, unexpected AE, unexpected SAE, AE of geriatric, renal disorder, hepatic disorder will be listed for safety analyses set. For subjects excluded from safety analysis set*, the number of subjects and the number of

unexpected AE/ADR, Serious AE (SAE)/Serious ADR (SADR), unexpected SAE/SADR, AE/ADR will be calculated according to the preferred terms. Also, the proportion of subjects to whom AE occurred will be estimated.

- * Subjects excluded from safety analysis set: Subjects excluded from safety analysis set except for ‘Subjects who didn’t receive Duavive tab.’ and ‘Follow-up failure: Subjects for whom adverse event status (Adverse Events status is unknown or missing) could not be established’.

Note: Unexpected AEs/ADRs will be classified by medical review and with reference to the local product document. Terms already included in the local product document are classified as ‘expected’. All other terms that are not included in the local product document will be classified as ‘unexpected’.

- The subjects with SAE, unexpected AE, unexpected SAE, AE of geriatric, renal disorder, hepatic disorder will be listed for subjects excluded from safety analyses set.

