7.3. Variables

7.3.1. Safety Variables

The type of adverse events (adverse event name), incidence rate, duration (start date and recovery date), severity, measures taken for the adverse event, results and causal relationship with Duavive tab. (based on the investigator's assessment), seriousness and predictability will be investigated in this study.

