7.3.1.1. Collection of Adverse Events Data

Please refer to Section 9 for the definition of adverse event (AE) and serious adverse event (SAE).

All AEs occurring within the adverse event reporting period will be recorded on the CRF by the investigator after the investigator reviews each subject's medical data.

Check either 'Yes' or 'No' in the AE section of CRF. If 'Yes', record the details.

- Adverse event: Record the pertinent name of the AE. Record the name of the AE by selecting an appropriate term among the Preferred Terms of the MedDRA. If no appropriate terms are found, use an optimal term listed in the Medical Terminology Dictionary (Korean Medical Society).
- Date of onset: Record the onset date of the AE. Record an approximate date if the actual date is unknown.
- Severity: Severity of the AE must be evaluated according to the following categories:
 - Mild: Not causing any significant problem to the subject. Administration of medicinal product continues without dose adjustment.
 - Moderate: Causing a problem that does not interfere significantly with usual activities or the clinical status. Dose of the medicinal product is adjusted or other therapy is added due to the AE.
 - Severe: Causing a problem that interferes significantly with usual activities or the clinical status. The medicinal product is discontinued due to the AE.
- Measures taken in relation to Duavive tab.: Select among the following options:
 - Permanently discontinued
 - Temporarily discontinued or delayed
 - Dose reduced
 - Dose increased
 - No change
 - Not applicable
- Other measures: Other measure taken after the onset of an adverse event is to be indicated in the following pertinent number and its content is to be described.
 - Prescription of treatment drug (Record the details in the Concomitant Medications section)
 - Other (Provide details)
 - Untreated
- Seriousness: In response to the question 'Is any of the seriousness criteria applicable?', check either 'Yes' or 'No'. If 'Yes', enter an applicable number among the definitions of serious adverse events. When a death has been caused, enter the date of death.
- Outcome: The evaluation of outcome will include: Record the date of recovery in case of 'Recovered' or 'Recovered with sequelae'.

- Recovered
 - Recovered with sequelae
 - Recovering
 - Not recovered
 - Unknown

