7.7.2. Interpretation Method (Statistical Considerations)

The data collected from each investigator during the re-examination period will be analyzed. The evaluation of data is shown by summarizing the data mainly using descriptive statistics, etc.

Since the frequency of adverse events occurring during the re-examination period is the primary concern of this study, the frequency of each adverse event will be presented at a 95% confidence interval. The status of the onset of serious AEs/ADRs, unexpected AEs/ADRs, and serious and unexpected AEs/ADRs will be summarized in separate tables.

Unexpected AEs/ADRs will be classified by medical review with reference to the local product document. Events already included in the “Precautions for use” section of the local product document will be classified as “expected”. All other events that are not included in the “Precautions for use” section of the local product document will be classified as “unexpected”. The unexpected AEs include any events that may be symptomatically and pathophysiologically related to the events listed in the local product document, but differ from the labeled event because of greater severity or specificity.

Subgroup analysis will be conducted by factor considered necessary including demographics and baseline characteristics to identify the factors having effects on safety and efficacy.

Total number of participating institutions, number of enrolled and collected cases and number of cases included in the analysis will be presented in the summary table.

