9.5. Single Reference Safety Document

The local product document will serve as the SRSD during the course of the study, and the investigator will use it to assess all the safety events reported to Pfizer Safety during the course of this study.

The investigator must use the SRSD for prescribing purposes and guidance.

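### The SAP's definition of an unexpected adverse event omits the protocol's greater-severity-or-specificity clause, so unexpected events can be under-counted

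*SAP*

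**What the plan says.** Protocol 7.7.2 gives the rule in three steps.

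- Medical review decides: "Unexpected AEs/ADRs will be classified by medical review with reference to the local product document".
- The reference list is one section of that document: "Events already included in the “Precautions for use” section of the local product document will be classified as" expected, and everything else is unexpected.
- A further sentence keeps some events that resemble labelled ones in the unexpected group, namely those that are related to a listed event "but differ from the labeled event because of greater severity or specificity".

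The same section sets the output: "The status of the onset of serious AEs/ADRs, unexpected AEs/ADRs, and serious and unexpected AEs/ADRs will be summarized in separate tables". Protocol 7.3.1 lists the safety variables and ends with "seriousness and predictability will be investigated in this study".

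The Note in SAP 8.2.1.4 also starts from medical review and the local product document, but then sorts by term: "Terms already included in the local product document are classified as" expected, and all remaining terms are unexpected. It has no sentence on severity or specificity and does not limit the reference to the Precautions for use section. Nothing elsewhere in the SAP restores the clause, and the SAP revision history (section 1) does not list a change to this definition.

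**The concern.** The two documents give different answers for the same event. The protocol sorts events and the Note sorts terms. A known reaction that appears in a worse form than the label describes is one that the protocol wants marked as unexpected. Under the Note it takes the status of its term and is marked expected.

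The flag feeds several outputs in SAP 8.2.1.4: the counts of unexpected AEs/ADRs and unexpected SAEs/SADRs by preferred term, the subject listings, the corresponding output for women excluded from the safety analysis set, and, in the re-examination report, the table by label frequency category. SAP section 3 withholds only the last of these from the periodic reports, so the others carry the flag there too.

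Two consequences follow if the Note is applied as written. A non-serious but more severe form of a labelled event drops out of the unexpected AE listing, unless the woman is listed for another reason. A serious one stays in the SAE listing but can lose its unexpected status.

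**Working it through.** The documents state no figure on this point, so there is none to reproduce. The check is a comparison of the two rules, followed by an illustration of size.

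**Step 1: apply both rules to every type of event.** Three facts classify an event: whether it is in the Precautions for use section, whether it is anywhere in the local product document, and whether it is of greater severity or specificity than the labelled event. Being in Precautions implies being in the document, so six combinations are possible. Term matching is taken to be the same for both rules.

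| In Precautions | In document | Greater severity/specificity | Protocol 7.7.2 | SAP Note |
|---|---|---|---|---|
| no | no | no | unexpected | unexpected |
| no | no | yes | unexpected | unexpected |
| no | yes | no | unexpected | expected |
| no | yes | yes | unexpected | expected |
| yes | yes | no | expected | expected |
| yes | yes | yes | unexpected | expected |

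The rules agree on three rows and differ on three. In every disagreement the protocol says unexpected and the SAP says expected. The SAP's unexpected set is thus a subset of the protocol's:

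SAP count = protocol count − k, with k ≥ 0.

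**Step 2: which rows matter.** The last row is the main gap. Within a labelled term, the Note applied term by term gives an unexpected count of 0 whatever the severity of the cases. The specificity part is smaller, because a more specific event that codes to its own unlabelled term is unexpected under both rules. Rows three and four come from the wider reference in the SAP and are secondary. They matter only if the label names events outside Precautions for use, which cannot be checked here. The protocol's own scope is also mixed, since section 9.5 says "The local product document will serve as the SRSD during the course of the study".

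**Step 3: illustration of size.** All inputs except 600 are assumptions.

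- k = women whose only unexpected event becomes expected: 0 to 5 (assumed).
- N = 600 (enrolment minimum, protocol 7.5) or 500 (assumed size after the SAP 5.1 exclusions).
- Fall in the unexpected proportion = k/N.

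| k | N = 600 | N = 500 |
|---|---|---|
| 1 | 1/600 = 0.17 points | 1/500 = 0.20 points |
| 5 | 5/600 = 0.83 points | 5/500 = 1.00 points |

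For a single woman at N = 600, a row of 1/600 = 0.17% (exact 95% CI 0.004% to 0.93%) becomes 0/600 = 0% (0% to 0.61%).

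**Step 4: the condition on direction.** If the two rules matched terms differently, m women could become unexpected under the SAP because a labelled event was coded to a differently worded term. The net shift is then (m − k)/N. With m and k each from 0 to 5, it runs from −0.83 to +0.83 points at N = 600 and from −1.00 to +1.00 at N = 500. The one-way direction therefore holds only with the same matching.

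**The case against.** The best case for the SAP has five parts.

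- **Medical review is kept.** A reviewer could apply the protocol clause despite the Note. This stands as a limit on size: the effect may be nil. It does not remove the discrepancy, because the Note goes on to tell the reviewer how to sort, and by term.
- **The protocol sentence may cover only distinct events.** On that reading, a related but different event codes to its own unlabelled term and is unexpected under both rules. This is largely right for specificity. It does not fit severity, since the sentence covers any related event that exceeds the labelled one in severity, and such an event can share the labelled term.
- **The SAP may modify the protocol (protocol 7.7).** True, but nothing in the SAP presents this as a deliberate change.
- **The comparison needs the label.** Greater severity can be judged only where the label describes severity. This stands: the difference in wording is certain, and the number of events affected is not.
- **The consequences are limited.** SAP section 4 has no hypotheses or decision rules. Protocol 9.1 sends all SAEs to the sponsor within 24 hours whether or not they are expected. Severe cases also remain visible in the preferred-term tables by severity and in the table of all adverse events (SAP 8.2.3). All of this stands and is why the point is minor. Those cases are visible but not marked as unexpected, and that mark is what the required tables report.

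**Conclusion.** The concern holds, as a minor one. The two definitions differ, and with the same term matching the SAP's version can only lower the count of unexpected AEs/ADRs and of unexpected SAEs/SADRs. The effect is confined to the split between expected and unexpected; totals are unaffected. Its size is unknown and possibly zero. The illustrative falls of up to 0.83 points (N = 600) or 1.00 point (N = 500) rest on an assumed 0 to 5 reclassified women, and the N = 500 figure also on an assumed analysis-set size. In rows that hold very few women, one reclassified case can decide whether the row appears at all. Confidence is high for the difference in definition and its direction, but not for any particular size.

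**What to change.** Replace the Note in SAP 8.2.1.4 with the full definition from protocol 7.7.2, including the section reference and the severity-or-specificity sentence. Apply it event by event in the medical review already planned, comparing each event with its labelled description, and carry the resulting flag into every unexpected AE/ADR/SAE/SADR table and listing.

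The CRF severity grade should be one input to that judgement and not a mechanical rule, because protocol 7.3.1.1 defines the top grade partly by the action taken: "The medicinal product is discontinued due to the AE". If the simpler rule in the Note is what the sponsor intends, the SAP should say that it departs from 7.7.2 and why.

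The cost is one paragraph and a reviewer's judgement for each event under a labelled term. That judgement may be hard where the label gives no severity to compare with, and the unexpected count may come out slightly higher.

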8.2.2 Effectiveness Analyses

Final effectiveness will be analyzed based on the evaluation of investigator for clinical response. Effectiveness analyses will be conducted for each indication. Because both indications can be selected, subjects can include in effectiveness analysis in duplicate.

- 1) Treatment for moderate to severe vasomotor symptoms associated with menopause:

Subjects who were assessed as ‘improved’ in “effectiveness evaluation” would be considered as “Effectiveness” and ‘no change’, ‘aggravated’ in “effectiveness evaluation” would be considered as “Ineffectiveness”. The effectiveness rate at last visit, which is defined as the proportion of subjects classified as ‘effectiveness’ in the final effectiveness evaluation, will be estimated with its 95% confidence interval.

For at last visit, the effectiveness rate according to the baseline characteristics listed in categorized measurements of section 8.2.1.1 (except for “Main indication” item) will be analyzed. Chi-square test or Fisher’s exact test will be used for comparing between subcategories of each baseline characteristic. When more than 20% of expected frequency of the cell count is less than 5, Fisher’s exact test should be used instead of chi-square test.

The frequency and percentage of clinical response evaluation at 3 months (± 2 weeks), 6 months (± 2 weeks), last visit (‘Effectiveness (improved)’, ‘Ineffectiveness (no change, aggravated)’ will be summarized.

- 2) Prevention of post-menopausal osteoporosis:

Subjects who were assessed as ‘effective in prevention’ in “effectiveness evaluation” would be considered as “effectiveness” and ‘ineffective in prevention’ in “effectiveness evaluation” would be considered as “ineffectiveness”. The effectiveness rate at last visit, which is defined as the proportion of subjects classified as ‘effectiveness’ in the final effectiveness evaluation, will be estimated with its 95% confidence interval.

For at last visit, the effectiveness rate according to the baseline characteristics listed in categorized measurements of section 8.2.1.1 (except for “Main indication” item) will be analyzed. Chi-square test or Fisher’s exact test will be used for comparing between subcategories of each baseline characteristic. When more than 20% of expected frequency of the cell count is less than 5, Fisher’s exact test should be used instead of chi-square test.

The frequency and percentage of clinical response evaluation at 3 months (± 2 weeks), 6months (± 2 weeks), last visit (‘Effectiveness(effective in prevention)’, ‘Ineffectiveness(ineffectiveness in prevention)’) will be summarized.

Also, if laboratory test data can be collected, the follow-up data at last visit will be compared with baseline data.

- X-ray examination
- Bone density test record (Bone mineral density)
- Other blood test record related to resorption of bone and osteogenesis (Biochemical marker of bone turnover)

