Amendment 4.0	16 Sep 2015	Substantial Amendments	(1) 7.2.4. Study Procedure (2) 7.2.4.3. Status of Administration of Duavive Tab. (3) 7.3.2.1. Efficacy Evaluation (4) 7.7.1.3. Section Related to Efficacy	(1) The content of the follow-up for long-term administration subjects was added. (2) Since the long-term administration subjects are included, the definition of study end time was deleted. (3) The content of the evaluation for long-term administration subjects was added. (4) The efficacy interpretation section for long-term subjects was added.	To reflect the review opinion of MFDS on the collection of information related to the follow-ups for long-term administration subjects
Amendment 5.0	05 Aug 2016	Substantial Amendments	7.2.4.4. Status of Administration of Hormone therapy	The status of administration of Hormone therapy before the Duavive Tab. administration was added.	To add the contents whether the patients have an experience about Hormone therapy or not and the reason why the Hormone therapy was discontinued.
Amendment 6.0	24 Mar 2020	Administrative amendment	Cover	Change of Principal Investigator(s) of the Protocol	Change of of responsible colleague
		Administrative amendment	2. RESPONSIBLE PARTIES	Change of Principal Investigator(s) of the Protocol	Change of of responsible colleague
		Substantial Amendments	7.3.1.1. Collection of Adverse Events Data	Change of AE Coding Dictionary	Change of Coding Dictionary according to New Drug Re-examination Guidelines
		Substantial Amendments	7.6. Data Management	Change of AE Coding Dictionary	Change of Coding Dictionary according to New Drug Re-examination Guidelines

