7.2.4. Study Procedure

This study doesn't require a screening procedure. All the subjects who consented to participate in this study by being administered with Duavive tab. for the first time according to the local product document after the start of the study at a study site and by signing the data privacy statement and who don't fall under the exclusion criteria will be enrolled sequentially.

Since this study aims to collect data under usual clinical practice, Duavive tab. will be administered according to the investigator's prescription and Pfizer will not provide the investigational product. The investigators will collect data on the basis of the medical data obtained by observing from the time of initial administration of Duavive tab. until 3 months (± 2 weeks). If the subject does not complete 3 months (± 2 weeks) of treatment, its reason should be recorded and relevant data should be collected based on the medical data observed until the time of treatment discontinuation.

Study of long-term use: The subjects who have been administered Duavive Tab. for at least 6 months (± 2 weeks) will be evaluated additionally. The investigator will be recommended to evaluate the relevant subjects at 6 months (± 2 weeks) after the treatment.

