7.7.1.3. Item Related to Efficacy

- Treatment for moderate to severe vasomotor symptoms associated with menopause: The investigator's judgment on the improvement of symptom recorded during the treatment (improved, no change, aggravated) is summarized as descriptive statistics, and an effective ratio is provided by considering 'improved' as "Effective" and 'no change' and 'aggravated' as "Ineffective".
- Prevention of post-menopausal osteoporosis: The investigator's evaluation of preventive effect (effective in prevention, ineffective in prevention) based on the laboratory test results related to osteoporosis will be summarized as descriptive statistics, and the effective ratio will be presented by considering 'effective in prevention' as "Effective" and 'ineffective in prevention' as "Ineffective".
- Sub analysis can be conducted for each factor considered to have an effect on efficacy.
- If laboratory test data can be collected, the 3 months (± 2 weeks) follow-up data will be compared with baseline data. In case of the subjects who are administered Duavive tab. for a long time, i.e. for at least 6 months (± 2 weeks), the 6 months (± 2 weeks) follow-up data will be compared with the 3 months (± 2 weeks) follow-up data.

- X-ray examination result
- Bone density test record
- Other blood test record related to resorption of bone and osteogenesis

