8.2 STATISTICAL ANALYSES

8.2.1 Safety Analyses

8.2.1.1 Baseline Characteristics

Baseline characteristics for this study are defined as follows:

- Continuous measurements will be presented Mean (SD) :
 - Age
 - Duration of disease[†]
 - Total administration period of Duavive tab.[‡]
- Categorized measurements will be presented n(%) :
 - Main indication (Treatment for moderate to severe vasomotor symptoms associated with menopause, Prevention of post-menopausal osteoporosis, both)
 - Geriatric status (<65 years, ≥65 years)
 - Age (<50 years, ≥50 years and ≤59 years, ≥60 years and ≤69 years, ≥70 years*)
 - Allergy history (Yes, No)
 - Duration of disease[†] (<3 months, ≥3 months and <6 months, ≥6 months*)
 - Medical history (Past disease, Present disease/Yes, No)
 - Total administration period of Duavive tab. (<3 months, ≥3 months and <6 months, ≥6 months*)
 - Long-term administration (<22 weeks, ≥22 weeks of total administration period of Duavive tab.)
 - Kidney disorder (Yes, No)
 - Liver disorder (Yes, No)
 - Concomitant medication (Yes, No)
 - Hormone therapy related to menopause before administration of Duavive Tab. (Yes, No)

[†] Only if main indication is “Treatment for moderate to severe vasomotor symptoms associated with menopause”

Duration of disease (months) = (number of years after diagnosis)×12+(number of months after diagnosis)

[‡] Total administration period of Duavive tab.= Sum of each administration period

: Each administration period = (Administration end date) – (Administration start date) + 1

If the medication is being continued at the completion of the study, administration end date is replaced with effectiveness evaluation date at last visit.

* The categories can be altered depending on the data distribution.

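### For the bone tests, the SAP replaces the protocol's 3-month and 6-month comparisons with one undefined last-visit comparison and does not note the change

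*SAP*

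**What the plan says.** Protocol 7.7.1.3 covers three kinds of test for the osteoporosis indication: X-ray, bone density, and blood tests of bone resorption and formation. If such data can be collected, "the 3 months (± 2 weeks) follow-up data will be compared with baseline data". For women treated for at least 6 months, "the 6 months (± 2 weeks) follow-up data will be compared with the 3 months (± 2 weeks) follow-up data".

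SAP 8.2.2, part 2, lists the same three tests under the same condition and plans one comparison: "the follow-up data at last visit will be compared with baseline data". No other SAP section plans the 3-month comparison, the 6-month against 3-month comparison, or a split of the test values by duration of use.

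Two kinds of follow-up feed into last visit. Under protocol 7.2.4, data come from "observing from the time of initial administration of Duavive tab. until 3 months (± 2 weeks"), and then: "The subjects who have been administered Duavive Tab. for at least 6 months (± 2 weeks) will be evaluated additionally".

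For the investigator's osteoporosis rating, the SAP keeps the separate times: "The frequency and percentage of clinical response evaluation at 3 months (± 2 weeks), 6months (± 2 weeks), last visit" are all to be summarised. It also keeps a duration split among the baseline characteristics, "Long-term administration (<22 weeks, ≥22 weeks of total administration period of Duavive tab"), which is used for adverse event and effectiveness rates.

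**The concern.** The bone tests are the objective measurements behind the osteoporosis indication. Under protocol 7.3.2.1 the investigator's rating at each time rests on them. With the SAP as written, the report would give the rating by time but the tests behind it only as one pooled figure.

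That figure mixes women whose last evaluation is at 3 months with women who stayed on treatment to 6 months. Its value would shift with retention even if nothing about the drug's effect changed. If women who continue differ from those who stop, duration and selection are also mixed. The protocol's 6-month against 3-month comparison is made within the same women and avoids this.

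The change looks like an oversight. Protocol Amendment 4.0 (16 Sep 2015) followed a review opinion of the regulator, and its log records: "The efficacy interpretation section for long-term subjects was added". SAP version 1.0 is dated later (04 Apr 2016), and no entry in the SAP's version table mentions leaving these comparisons out.

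**Working it through.** The documents give no effect size, power or sample size for the bone tests, so there is no figure to reproduce. The check is a comparison of texts, followed by an illustration on assumed values.

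**Step 1: planned comparisons of the test values.**

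| Comparison | Protocol 7.7.1.3 | SAP 8.2.2(2) |
|---|---|---|
| 3 months vs baseline | yes | no |
| 6 months vs 3 months, long-term users | yes | no |
| Last visit vs baseline | no | yes |

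**Step 2: are the two times distinct?** With 4-week months the windows are 3×4 ± 2 = 10 to 14 weeks and 6×4 ± 2 = 22 to 26 weeks. With calendar months they are about 11 to 15 and 24 to 28 weeks. They do not overlap on either count, so last visit pools two separate times. The 4-week version also gives the SAP's own 22-week cut for long-term use.

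**Step 3: what the pooled mean estimates.** Let d3 and d6 be the mean changes from baseline at 3 and 6 months, and f the share of tested women whose last visit is the 6-month one. For simplicity, assume the same d3 in women who continue and women who do not. Then

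pooled change = (1 − f)·d3 + f·d6.

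All inputs are assumed. With d3 = d:

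| f | d6 = d | d6 = 1.5d | d6 = 2d |
|---|---|---|---|
| 0.2 | 1.0d | 1.1d | 1.2d |
| 0.4 | 1.0d | 1.2d | 1.4d |
| 0.6 | 1.0d | 1.3d | 1.6d |

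For example, at f = 0.4 and d6 = 2d: 0.6×d + 0.4×2d = 1.4d. If d6 = d, pooling does not move the mean. Otherwise the mean moves with f.

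**Step 4: can the time-specific results be recovered?** Suppose the pooled change is 1.3d. Even if d3 were known to be d, solving for d6 gives d6 = d + 0.3d/f:

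- f = 0.2: d6 = 2.5d
- f = 0.3: d6 = 2.0d
- f = 0.4: d6 = 1.75d
- f = 0.6: d6 = 1.5d

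One pooled value therefore fits many 6-month results. In practice d3 is unknown as well, so the pooled figure alone gives neither the 3-month change nor the change from 3 to 6 months.

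**The case against.** The strongest reply is that the change is permitted and small. Protocol 7.7 lets the SAP modify the plan and requires a protocol amendment only for major changes to primary endpoint definitions or their analyses. Protocol 7.7.2 names adverse event frequency as the primary concern. The bone tests are analysed only if collected, no visit is mandated, the 6-month evaluation is only recommended, and SAP section 4 sets no hypotheses or decision rules. The 6-month against 3-month comparison needs tests in both windows from the same woman, and the documents do not say how many such pairs to expect. All of this stands and limits the weight of the point. It does not make a pooled figure readable by time.

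A reader might infer that the SAP abandons the long-term effectiveness evidence. The documents do not support that. The investigator's rating is still tabulated at 6 months, effectiveness rates are still split at 22 weeks of use, and 6-month test values still enter as last-visit data.

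A reader might also infer that the tests are summarised at no identifiable time. That goes too far. The protocol's evaluation times are 3 and 6 months, and SAP 8.2.2 ties the last-visit effectiveness rate to the final evaluation. The pooling is therefore mainly over two known windows. What is missing is a definition of last visit for the test values.

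Finally, the arithmetic rests on assumed ratios and shares. It shows how the pooled figure behaves and does not estimate a bias in this study.

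**Conclusion.** The point holds for the bone tests only. Both texts are current, and the SAP omits the protocol's two time-specific comparisons, substitutes a pooled one, and does not say so. What is lost is the summary of test values at 3 months against baseline and at 6 months against 3 months.

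The size cannot be stated from the documents. It is zero for the mean if the 3-month and 6-month changes are equal, and it grows with their difference and with the share of long-term users. The illustration assumes the same 3-month change in continuers and non-continuers. If that fails, selection is mixed in as well.

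This is not a protocol breach that required an amendment, and it does not touch the safety analysis. It is a conditional, secondary, descriptive item that should be corrected because the correction is cheap and brings the test values into line with the times the SAP already uses for the ratings.

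**What to change.** In SAP 8.2.2(2):

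1. Restore the paired comparison of 3 months with baseline.
2. Restore the paired comparison of 6 months with 3 months, in women with at least 6 months of use.
3. For each, give the number of pairs and the SAP 8.1.1 descriptive statistics of the change. X-ray results recorded as categories can follow SAP 8.1.2. A 95% confidence interval for the mean change is optional, since the protocol does not plan one.
4. Define last visit for the test values, including whether it means the last evaluation attended or the last available result of each test. Keep that comparison as supplementary.

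If the sponsor prefers the last-visit comparison alone, the SAP should state the departure from protocol 7.7.1.3 and give the reason.

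The cost is a few sentences and two small tables. Protocol 7.3.2.1 already provides for test results at baseline, 3 months and 6 months where they exist, so no new data are needed. The SAP version 3.0 entry still shows its revision date as to be determined, so the text can go into that version if it is not yet final.
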